4.1. Objective

To gather data on the long-term safety of ReActiv8 and identify any residual risks by reporting all Serious Adverse Device Effects as well as performance and health care utilization through two years post-implant.

4.2. Overview

The ReActiv8 Registry is an international, multi-center, data collection registry in Subjects who meet the CE Mark indications and are not contraindicated for ReActiv8. A minimum of 50 Subjects will be implanted at up to 25 sites. Subjects will be followed for two years postimplant, at which time they will be exited from the Registry. Subjects may decide to be enrolled in the registry before or after implant so that information on the performance of the system can be collected.

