4.7. Data Collection Schedule

The data for the registry will be collected according to the following schedule:

Visit 1: Baseline visit

Visit 2: Activation visit (approximately 14 days post-surgery)

Visit 3: 90±30 days Post-Activation

Visit 4: 180±30 days Post-Activation

Visit 5: 1 year±60 days Post-Activation

Visit 6: 2 years ±60 days Post Activation

The above mentioned visits are part of the standard of care for patients with this type of treatment. The given time windows are advisable and data collection outside these windows will not be seen as a protocol deviation.

Any unscheduled visits will be recorded as stated in Table 3 and in section 4.7.6.

Note that data collection of all performance measures shall be done as the first thing in the follow up visit, prior to any other procedures.

Note that once a Subject has consented to participate in the Registry Adverse Events will be collected at each visit.

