4.7.1. Visit 1: Baseline Visit

The process for obtaining informed consent shall be in compliance with ISO 14155.

If the subject agrees to participate in the registry for data collection, the Subject Informed Consent will be signed and recorded in the Subject's records at Visit 1. The Subject will be assigned a unique Registry identifier and will be asked to complete the baseline questionnaires.

Data will be collected according to the data collection schedule (Table 3).

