4.7.2. Visit 2: Activation Visit (≈ 14 days Post Implant)

Activation of the therapy shall be about 14 days from the date of implant surgery.

If the Subject is unable to use the device for any reason (e.g.: injury, infection, other new clinical condition) at the time of the activation visit, then the activation visit may be postponed to allow the issue to resolve. This will not be considered a deviation.

Activities to be performed:

- Perform electrode impedance and threshold measurements and record results
- Program IPG
- Train the Subject in use of the Activator, and document assessment of Subject's ability to self-administer therapy. Instruct Subject on timetable of therapy delivery (i.e.: twice a day starting the next day).
- Train the Subject in the procedure to deliver stimulation, including time of day and Subject positioning.

Data will be collected according to the data collection schedule (Table 3).

Visits 3 and 4: 90 ± 30 Days and 180 ± 30 Days Post 4.7.3. Activation

During this visit data will be collected according to the data collection schedule (Table 3) and the following activities will be performed:

Device activities (if applicable):

- Electrode impedance and threshold measurements
- Readout from IPG of therapy delivery times and duration
- Adjustment of stimulation configuration and amplitude as appropriate

If a subject is unable to return to the clinic for an annual office visit, the clinical site may send the questionnaires to the subject for completion and a telehealth visit may be completed by the investigator and study coordinator.

Device interrogation and programming will be done at a later date when the subject is able to return for a visit.

If programming is completed it will be entered on the annual visit form. It will not be a deviation when the interrogation and programming of the system is required at a later date.

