4.7.6. Unscheduled Visits

If an unscheduled visit occurs for any reason, the following data will be collected prior to any other activities.

- Low Back Pain NRS (average low back pain in the last 24 hours)
- Report Adverse Events (if applicable)
- Complete and document device activities if applicable

Data will be collected according to the data collection schedule (Table 3).

Table 3: Data Collection Schedule

	1: Baseline Visit	2: Activation Visit about 14 Days Post- Surgery	3: 90±30 Days Post Activation	4: 180±30 Days Post Activation	5: 1 Year ±60 Days Post Activation	6: 2 Year ±60 Days Post Activation	Unscheduled Visit
Medical History including Pain Detect Questionnaire	✓						
Low Back Pain (NRS)	✓	✓	✓	✓	✓	✓	✓
ODI	✓		✓	✓	✓	✓	
EQ-5D	✓		✓	✓	✓	✓	
Percent Pain Relief (PPR)			✓	✓	✓	✓	
Subject Global Impression of Change (SGIC)			✓	✓	✓	✓	
Treatment Satisfaction Questionnaire (TSQ)			✓	✓	✓	✓	
Work Status Evaluation	✓		✓	✓	✓	✓	
Medications: Opioids	✓		✓	✓	✓	✓	
Health Care Utilization	✓				✓	✓	
Device Measurements & Stimulation Thresholds*		✓	✓	✓	✓	✓	✓
Adverse Events (AE's)		✓	✓	✓	✓	✓	✓

^{*}Device information will be collected at the implant procedure.

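### Baseline is not anchored to implant, so Subjects enrolled after implant have a post-surgery reference for their change scores, PPR and SGIC

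*Protocol*

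**What the plan says.** Section 4.2 states "Subjects may decide to be enrolled in the registry before or after implant" and gives no maximum interval after implant. Section 4.9.1 requires consent before participation. Section 4.7.1 has consent signed at Visit 1 and continues: "The Subject will be assigned a unique Registry identifier and will be asked to complete the baseline questionnaires". The registry baseline is therefore taken at consent, whenever that falls.

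The other scheduled visits have a time origin. Visit 2 is timed from surgery (section 4.7.2: "Activation of the therapy shall be about 14 days from the date of implant surgery"), and Visits 3 to 6 are timed from activation. Visit 1 has no day, window or origin in section 4.7, section 4.7.1 or Table 3.

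The Registry Summary lists NRS, ODI, EQ-5D, work status and opioid use as changes from baseline. Section 4.5.4 refers PPR to the registry baseline, and section 4.5.5 asks SGIC as change since baseline. Section 4.6 and Table 3 also collect Health Care Utilization at baseline.

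Two further statements in section 4.7 matter. On the listed visits: "The above mentioned visits are part of the standard of care for patients with this type of treatment". On safety: "once a Subject has consented to participate in the Registry Adverse Events will be collected at each visit".

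**The concern.** The objective in section 4.1 includes performance through two years post-implant, and section 4.2 gives the collection of performance information as the reason for flexible enrolment. A reader will take change from baseline to mean change from the state before the device was implanted. For a Subject enrolled after implant (a late enrollee, below) it does not mean that.

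The starting state may differ in a way that matters. NRS covers only the preceding 24 hours (section 4.5.1). Section 4.4.2 itself expects incisional pain, muscle pain and sleep problems in the first days after surgery. ODI includes sections on lifting and sleeping (section 4.5.2), which recent surgery may affect. If a late enrollee's baseline were taken after stimulation had begun, it could already contain part of the response.

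This is a data collection problem before it is an analysis problem. An analysis plan can separate or exclude late enrollees. It cannot supply pre-implant values that sites were never asked for, and it cannot change the reference point of PPR and SGIC once Subjects have answered.

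**Working it through.** **1. The plan's own figure.** Section 4.8 gives 80% power to see at least one event with 50 Subjects at a rate of 3.2%. Check: 1 − (1 − 0.032)^50 = 0.803. The figure reproduces. It concerns event detection only and is not affected by this point.

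**2. Which measures depend on baseline.** The Registry Summary lists 6 performance measures (NRS, ODI, EQ-5D, PPR, SGIC, TSQ) and 3 health care utilization measures (work status, opioids, Health Care Utilization), 9 in all.

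| Measure | Use of baseline | Baseline tick in Table 3 | Visit 2 tick |
|---|---|---|---|
| NRS | change | yes | yes |
| ODI | change | yes | no |
| EQ-5D | change | yes | no |
| Work status | change | yes | no |
| Opioids | change | yes | no |
| PPR | reference point of a retrospective question | no | no |
| SGIC | reference point of a retrospective question | no | no |
| Health Care Utilization | collected at baseline and annual visits | yes | no |
| TSQ | none | no | no |

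- Defined against baseline: 5 change measures + 2 retrospective questions = 7 of 9.
- Health Care Utilization is assessed at follow-up in the Registry Summary, but its baseline record is also post-surgery for late enrollees. Only TSQ is untouched.
- Of the 5 change measures, 1 (NRS) is read at Visit 2, so 5 − 1 = 4 have no second scheduled reading before the 90-day visit.
- PPR and SGIC have no baseline reading at all, so they do not belong in that last count.

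**3. Can the Visit 2 NRS stand in?** Section 4.7 requires "data collection of all performance measures shall be done as the first thing in the follow up visit, prior to any other procedures". If Visit 2 counts as a follow-up visit, its NRS comes before programming. It is still taken about 14 days after surgery, and it covers one measure.

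**4. How late can baseline be?** The numbering puts Visit 1 before Visit 2, which suggests that baseline precedes activation, roughly within two weeks of surgery. No sentence requires this. Section 4.2 sets no limit, and section 4.7.2 lets activation be postponed.

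**5. Size.** For one late enrollee, if the registry baseline differs from the pre-implant value by s, the change score is off by exactly s. If late enrollees made up a share f of a combined mean, and s were their mean shift, the error would be f × s. The documents give neither f nor s. The values below are assumptions to show scale on the NRS only.

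| f (assumed) | s = ±1 point | s = ±2 points |
|---|---|---|
| 10% | ±0.10 | ±0.20 |
| 25% | ±0.25 | ±0.50 |
| 50% | ±0.50 | ±1.00 |

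The sign is open. Surgical pain could raise the baseline and inflate improvement. Post-operative analgesia, or a baseline taken after therapy started, could lower it and understate improvement.

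**The case against.** The case for leaving the text alone has several parts.

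- **No pooled analysis is stated.** A reader might infer that the protocol combines pre-implant and post-implant baselines in one analysis. It does not say so. It lists measures and has no analysis section, and separating late enrollees is ordinary SAP content. This stands. What remains is that the protocol does not distinguish the two kinds of baseline and does not collect what a SAP would need to repair the second kind.
- **Visit order limits the exposure.** If Visit 1 always precedes activation, a late baseline is taken before stimulation and soon after surgery. This is a fair reading and may narrow the problem, but it is implied only, and the baseline is still post-surgery.
- **Routine records may hold earlier values.** Section 4.7 calls the listed visits standard of care, so some pre-implant values may exist. The protocol does not ask for them, and nothing shows that ODI or EQ-5D would be among them.
- **Enrolment timing is already derivable.** Consent is personally dated (section 4.9.1), device information is collected at implant (Table 3 footnote), and activation is a registry visit. This stands, so a derived flag is enough.
- **The registry is led by safety.** The sample size rests on event detection, there is no comparator or performance hypothesis, and enrolment after implant is a deliberate choice. This limits the weight of the point but does not make the change measures interpretable for late enrollees.

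**Conclusion.** The point holds and should be fixed. Under the text as written, a Subject enrolled after implant has a post-surgery starting point for five change measures, a post-surgery reference for PPR and SGIC, and a post-surgery baseline Health Care Utilization record. This follows from sections 4.2, 4.5.4, 4.5.5, 4.6, 4.7.1 and Table 3 without further assumption.

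The effect is confined to late enrollees. Subjects enrolled before implant, and TSQ, are not affected. The size of the bias is unknown because the number of late enrollees and the shift in their scores are not given; the f × s table rests wholly on assumed values and on a combined mean that the protocol does not prescribe. A reader might also infer that the arrangement favours the device. The documents do not support that, since the shift could go either way.

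**What to change.** In sections 4.2, 4.7 and 4.7.1:

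- Define baseline for NRS, ODI, EQ-5D, work status and opioid use as the last assessment before implant, and label the baseline Health Care Utilization record in the same way.
- For late enrollees, use pre-implant values from source records where they exist.
- Word PPR and SGIC (sections 4.5.4 and 4.5.5) to refer to the state before implant.
- Flag each Subject as enrolled before or after implant, derived from the consent, implant and activation dates.
- State, in the protocol or the SAP, that late enrollees without a pre-implant value are reported separately from the main change-from-baseline summaries.
- Keep late enrollees in the safety reporting, with a note that adverse event collection starts at consent, so events around implant that preceded it may be missed.

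The cost is an amendment under the local approval rules in section 6.1 and some record extraction by sites, which may not yield ODI or EQ-5D. The main change tables would hold fewer Subjects, and PPR and SGIC would carry some recall error for late enrollees. Flexible enrolment itself can stay.

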4.3. Enrolment Criteria

4.3.1. Inclusion Criteria

In order to be included in this Registry, Subjects must meet the following inclusion criteria:

- 1. Meet the Indications for ReActiv8
- 2. Willing to sign the Informed Consent for the ReActiv8-C Post-Market Surveillance Registry
- 3. Age ≥ 18 years

4.3.2. **Exclusion Criteria**

Subjects will be excluded from the Registry if they are contraindicated for ReActiv8.

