Safety, Performance, Health Utilization Measures	 Assessment of all Serious Adverse Device Effects that occur through two years post-implant. Performance Change in average low back pain from baseline to follow-up visits (NRS) Change in Oswestry Disability Index from baseline to follow-up visits (ODI) Change in EQ-5D from baseline to follow-up visits (EQ-5D) Assessment of Percent Pain Relief at follow-up visits (PPR) Assessment of Subject Global Impression of Change at follow-up visits (SGIC) Assessment of Patient Treatment Satisfaction at follow-up visits (TSQ) Health Care Utilization Change in work status from baseline to follow-up visits Change in use of opioids from baseline to follow-up visits Assessment of Health Care Utilization (office visits, hospital visits, imaging and diagnostics and other pain management treatments) at follow-up visits 						
Study Visit Schedule	 Visit 1: Baseline visit Visit 2: Activation visit: Approximately 14 days post-surgery Visit 3: 3 month visit: 90±30 days post-activation Visit 4: 6 month visit: 180±30 days post-activation Visit 5: 1 year visit: 1 year±60 days post-activation Visit 6: 2 year visit: 2 year±60 days post-activation 						

2. Background

Mainstay Medical has developed an implantable medical device designed as therapy for people with chronic low back pain (CLBP). The device, called ReActiv8®, consists of two implantable leads with four electrodes each, configured to deliver electrical stimulation to the medial branch of the dorsal ramus nerves as they cross the transverse process at L3 to elicit bilateral contraction of the lumbar multifidus muscles (MF). The leads are coupled to a battery powered implantable pulse generator (IPG) which is activated by an external Activator and is programmed using Application Software provided on a laptop computer. Several accessories are included as part of the system, for example to facilitate the surgical procedure.

The therapy delivered by the ReActiv8 was explored with a European Feasibility Study in 2011 to 2013 using "off the shelf" general purpose neurostimulation devices from other manufacturers, and results have been published.¹

ReActiv8 was investigated under an ongoing clinical trial at nine sites in Australia and Europe (ReActiv8-A). The data from the first 47 Subjects implanted with ReActiv8 in this trial served as the basis for CE Marking on 24-May-2016. A summary of the ReActiv8-A Trial can be found at http://clinicaltrials.gov/show/NCT01985230.

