3.3. Contraindications

ReActiv8 is contraindicated for patients who are:

- Unable to operate the system
- Unsuitable for ReActiv8 implant surgery

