4.8 Sample Size Rationale

The sample size was based on the desire to gain a sufficient amount of representative data with the device in the market-released setting. In order to more fully characterize the experience with the system and detect rare events, the sample size of 50 Subjects provides 80% power to observe the incidence of at least one rare event for any events occurring at a population rate as low as 3.2%.

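### Section 4.2 allows enrolment before or after implant with no latest time and no consecutive-invitation rule, so entry can depend on an early outcome already known and the 80% detection statement is not secured

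*Protocol*

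**What the plan says.** Entry requires the indication, willingness to consent and age 18 or over (Protocol 4.3.1). The single exclusion, in 4.3.2, is: "Subjects will be excluded from the Registry if they are contraindicated for ReActiv8". Section 3.3 lists two contraindications: "Unable to operate the system" and "Unsuitable for ReActiv8 implant surgery". Neither concerns an existing implant or how it has gone.

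On timing, Section 4.2 says: "Subjects may decide to be enrolled in the registry before or after implant so that information on the performance of the system can be collected". It gives no maximum time since implant and no rule on which implanted patients are to be approached. The same section says: "A minimum of 50 Subjects will be implanted at up to 25 sites". Follow-up ends two years after implant.

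Section 4.7 and Table 3 order the visits as baseline, then activation about 14 days after surgery, then follow-up timed from activation. Section 4.7 calls the time windows advisable and starts adverse event collection once the Subject has consented. Section 4.7.1 places consent and the baseline questionnaires at Visit 1. Section 4.7.2 lets activation be postponed.

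The sample size rationale in 4.8 begins: "The sample size was based on the desire to gain a sufficient amount of representative data with the device in the market-released setting". It then claims 80% power to observe at least one event of a kind that occurs at a population rate as low as 3.2%, with 50 Subjects.

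**The concern.** A registry that claims representative market-released data needs entry that does not depend on outcome. Under 4.2 as written, a site may look back over patients it has already implanted and invite some of them. Someone with an early infection, an explant or no benefit is less likely to be invited or to accept. A site could even read the second contraindication as ruling out a patient who has had such a complication, since 4.3.2 does not say at what time suitability is judged.

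Two losses follow. Some patients with early events never enter. For those who do enter late, events before consent fall outside the collection rule in 4.7. Both act on the objective in 4.1, which is to identify residual risks by reporting serious adverse device effects (SADEs). An analysis plan cannot recover patients who were never invited, so the rule belongs in the protocol.

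**Working it through.** **The protocol's own figure.** Inputs from 4.8: n = 50, rate p = 0.032, at least one event.

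- P(at least one) = 1 − (1 − p)^n = 1 − 0.968^50 = 0.803, which agrees with the stated 80%.
- Smallest rate seen with 80% probability: 1 − 0.2^(1/50) = 3.17%.

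The formula treats all 50 Subjects as observed throughout the time when the event can occur.

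**Effect of late entry on detection.** Let k of the 50 enter after the period in which the event occurs, so that they cannot show it. Then P = 1 − 0.968^(50 − k), and the rate detectable with 80% probability is 1 − 0.2^(1/(50 − k)). The protocol does not give k; the values are assumed.

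| k late of 50 | Chance of at least one event at 3.2% | Rate detectable with 80% probability |
|---|---|---|
| 0 | 80.3% | 3.2% |
| 10 | 72.8% | 3.9% |
| 25 | 55.7% | 6.2% |
| 40 | 27.8% | 14.9% |

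If only half of the event risk falls before consent in late entrants, P = 1 − 0.968^(50 − k) × (1 − 0.016)^k. This gives 76.8% for k = 10 and 70.4% for k = 25. For events that arise after consent there is no loss of this kind.

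**Effect on the SADE proportion.** Assume that 10% of implants have an early explant. Let s be the share of Subjects enrolled late, and r the chance that an explanted patient enrols late relative to one without an explant. Among late entrants the proportion is 0.10r / (0.10r + 0.90).

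- r = 0: 0% among late entrants. Overall 0.8 × 10% = 8% for s = 0.2, and 0.5 × 10% = 5% for s = 0.5.
- r = 0.5: 0.05 / 0.95 = 5.3% among late entrants. Overall 9.1% for s = 0.2, and 7.6% for s = 0.5.

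**Effect on satisfaction (TSQ).** This yes/no item has no baseline. Assume that 50% are truly satisfied and that satisfied patients are twice as likely to be enrolled late. Among late entrants: 0.5 × 2 / (0.5 × 2 + 0.5 × 1) = 66.7%. Overall: 0.8 × 50% + 0.2 × 66.7% = 53.3% for s = 0.2, and 58.3% for s = 0.5.

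**Effect on the other performance measures.** The Registry Summary defines NRS, ODI and EQ-5D performance as change from baseline. Sections 4.5.4 and 4.5.5 anchor PPR and SGIC to baseline as well, and 4.5.4 specifies baseline in the Registry. Under 4.7.1 that baseline is completed at Visit 1, the visit at which consent is signed. A late entrant who is already doing well starts from a good score, and the improvement before consent is not counted. Selecting such patients would therefore probably shrink these effects.

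**The case against.** The strongest reply is the visit order. Baseline precedes activation, activation is about 14 days after surgery, and 4.2 speaks of Subjects who will be implanted. If that order is followed, late entry is confined to roughly two weeks (longer if activation is postponed), and already-activated patients do not fit. This stands as a reason to think that late entry may be small. It is not an eligibility rule, however: 4.2 expressly permits enrolment after implant, and 4.7 calls the windows advisable. A site enrolling an activated patient would breach no stated criterion. Even within two weeks, a perioperative complication can be known before the invitation.

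It is also fair that the late share, the explant rate and the strength of selection are assumed. The figures above show sensitivity, not an estimate. Consecutive logging can be called good practice, but here its absence leaves the claim in 4.8 unprotected.

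Three stronger readings are tempting and not supported:

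- **That the cohort is not the market-released population.** The protocol shows only that it need not be; the number enrolled late is unknown.
- **That participants in the pre-market ReActiv8-A trial could fill the 50.** Section 2 mentions that trial only as background: "The data from the first 47 Subjects implanted with ReActiv8 in this trial served as the basis for CE Marking". Their entry is inferred from silence. It fits poorly with the wording that Subjects will be implanted and with exit two years after implant, which leaves little or no follow-up for older implants. Later implants in that trial, described as ongoing, may exist, but nothing links them to the Registry.
- **That pain and disability results would look too favourable.** Against registry baseline, the opposite is more likely.

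**Conclusion.** The point holds in a limited form. The enrolment rule in 4.2 lets entry depend on what has already happened to the patient, and it is not reconciled with the visit order in 4.7. The likely direction is a SADE proportion that is too low and satisfaction that is too high, with change-from-baseline measures distorted, probably downwards in late entrants who already do well.

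The 80% statement in 4.8 is arithmetically correct but conditional on observing all 50 from implant. For an event confined to the time before late entry, it becomes about 73% with 10 late entrants and 56% with 25. If nobody enters late, there is no loss. Whether the Registry is in fact unrepresentative cannot be settled from the protocol.

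**What to change.** Amend 4.2 to state that:

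- a Subject may be enrolled no later than Visit 2, before first activation, so that entry cannot depend on response to therapy;
- from site opening, every commercial ReActiv8 implant is entered on a site log and invited consecutively, including patients with a complication or explant before Visit 2;
- the numbers implanted, invited and enrolled are reported.

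The cut-off alone does not remove selection on surgical complications between implant and Visit 2; the log is what addresses that. Because 4.7 starts adverse event collection at consent, events since implant should also be recorded for anyone who consents after implant. Otherwise the 80% statement still does not cover that interval.

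A clause saying whether pre-market trial participants are eligible is optional clarification.

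The cost is a few sentences in an amendment and a one-page log per site. The downside is that already-activated patients cannot enter, so accrual may be slightly slower.
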